**REVISION HISTORY**

Version No.	Effective Date	Summary of Change(s)
1.0	16JUL2020	New document
2.0	05JAN2022	
1. Update SAP per new version of Protocol (Final, 16-Sep-2020; Amendment 3 (Version 4.0))
 
 
• Change of Title to include 'WHO grade 3 & 4'
 
• Modify Primary Objective/Endpoint for addition of WHO grade 3 or grade 4.
 
• Modify Secondary Objective/Endpoint for addition of WHO grade 3 or grade 4
 
• Change of wording accordingly to refer to use of supplemental oxygen 'if applicable' because WHO grade 3 do not require supplemental oxygen, so not all study patients will be using supplemental oxygen.
 
• Exclusion criterion 13 updated to specify that mHb >1% is exclusionary
 
• Amendment of Methb threshold from 1% to 2%
 
• Schedule of Activities: Changed description of oxygen measurements pre/post treatment to make clearer and remove repetition
 
• nebulization from 4 minutes to 8
 
 
2. Add/modify few abbreviation

**LIST OF ABBREVIATIONS**

Abbreviation / Acronym	Definition / Expansion
ADaM	Analysis Data Model
ADI	Actual Dose Intensity
AE	Adverse event
ANCOVA	Analysis of Covariance
BMI	Body Mass Index
BP	Blood pressure
CHW	Cui/Hung/Wang
CI	Confidence interval
CMH	Cochran Mantel Hensel
COVID-19	Coronavirus disease 2019
CP	Conditional Power
DBP	Diastolic blood pressure
DoD	Date of Discharge
DRE	Disease Related Events
ECG	Electrocardiogram
FiO2	Fraction of Inspired Oxygen
IDI	Intended Dose Intensity
IDMC	Independent Data Monitoring Committee
ITT	Intent-to-Treat
IVRS	Interactive Voice Response System
IWRS	Interactive Web Response System
LOCF	Last Observation Carried Forward
MedDRA	Medical Dictionary for Regulatory Activities
mHb	Methemoglobin
MMRP	Mixed Model Repeated Measures
NCI	National Cancer Institute
NEWS	National Early Warning Score
PP	Per Protocol Population
PT	Preferred Term

# PAREXEL International

30 Respiratory Limited  
RESP301

Statistical Analysis Plan

Abbreviation / Acronym	Definition / Expansion
RBC	Red Blood Cells
RDI	Relative Dose Intensity
SAP	Statistical Analysis Plan
SAE	Serious adverse event
SBP	Systolic blood pressure
SD	Standard Deviation
SOC	System Organ Class
SP	Safety Population
SpO 2	Oxygen Saturation
TID	Three Times a Day
WBC	White Blood Cells
WHO	World Health Organization

CCI  
CCI  
CCI

CONFIDENTIAL

Project Document Version No. 2.0  
Project Document Effective Date: Date of last signature  
Page 7 of 31

## 1 INTRODUCTION

Coronavirus disease 2019 (COVID-19) is a respiratory illness caused by a novel coronavirus (SARS-CoV-2). COVID-19 was first described in Wuhan, China, in December 2019 and is now a global pandemic (Matos et al, 2020). Most of those affected have milder illness (80%), 15% will be severely ill (require oxygen) and 5% will require intensive care unit care (Novel Coronavirus Pneumonia Emergency Response Epidemiology Team, 2020). Of those who are critically ill, most require early intubation and mechanical ventilation.

A critical early component of innate host defense in the airway is the ability of respiratory epithelial cells to produce high levels of NO (Kao et al, 2001). NO functions as a signaling molecule in initiation of the inflammatory response to viruses, and also has direct antiviral effects (Folkerts et al, 1998).

RESP301 is a NO-generating liquid designed to release NO in situ in the upper airways and deep in the alveolar spaces. RESP301 is delivered via a handheld nebulizer and has specific advantages over inhaled NO gas in treating patients with COVID-19 during the current pandemic.

This is an open-label, randomized, multicenter, parallel group, concurrent, controlled study using a sequential adaptive design. Participants will be consented and randomized 2:1 to the Investigational arm or the Control arm. Participants randomized to the Investigational arm will receive inhaled RESP301 (6 mL) administered using a nebulizer 3 times a day (TID) for up to 10 days in addition to the standard of care (SOC) while participants in the Control arm will receive SOC alone.

The analyses described in this SAP are based upon the following study documents:

- Study Protocol, Version 4.0 (September 16, 2020 )
- electronic Case Report Form (eCRF), Version 3.0 (June 24, 2020)
- RESP301 DMC Charter

## 2 STUDY OBJECTIVES

### 2.1 Primary Objective

- To evaluate efficacy of RESP301 in preventing progression of hospitalized COVID-19 participants at level 3 or 4 in the modified World Health Organization (WHO) ordinal scale into higher levels.

### 2.2 Secondary Objectives

- To assess the effect of RESP301 as measured by room air SpO2
- To assess the effect of RESP301 as measured by the National Early Warning Score (NEWS) 2 symptom score

- To assess the treatment response on clinical status

## Additional Secondary Objectives

- To assess the overall safety profile of RESP301 in COVID-19 participants
- To assess the ability of participants to tolerate nebulization

## 2.3 Exploratory Objective

• CCI

### 3 INVESTIGATIONAL PLAN

### 3.1 Overall Study Design and Plan

This is an open-label, randomized, multicenter, parallel group, concurrent, controlled study using a sequential adaptive design to evaluate the efficacy and safety of RESP301 added to standard of care (SOC) in hospitalized patients with COVID-19 (WHO ordinal scale grade 3 & 4).

Central stratified randomization of 300 subjects to assign participants into one of the study treatment arms will occur as follows, RESP301+SOC or SOC (control), with a randomization ratio of 2:1 using an interactive voice response system (IVRS)/interactive web response system (IWRS). Participants will be stratified by country and presence of risk factors for severe outcomes of COVID-19, based on comorbidities and age as follows:

1. Age  $>65$  years
2. Ongoing or currently treated diabetes mellitus
3. Ongoing or currently treated hypertension
4. Ongoing or currently treated cardiovascular disease
5. Ongoing or currently treated chronic lung disease
6. Cancer history of less than 3 years, basal cell skin carcinoma excluded
7. Ongoing or currently treated chronic kidney disease

Participants will be stratified as no risk factor (none of the above criteria), one risk factor (one single of the above) or high-risk factor (2 or more of the above).

There are 3 phases in the overall study design: Screening Period, Intervention Period, Follow-up Period. Figure 1 displays the study schematic.

**Screening Period**– Patients will be screened up to 2 days prior to treatment administration. Upon signing informed consent, the patient enters the screening phase and is assessed for the inclusion/exclusion criteria. If all eligibility criteria are met, the patient moves into the intervention period.

[figure not shown]
**Intervention Period** – The intervention period starts on Treatment Initiation (Day 1). Patients will receive treatment three times a day up to Day 10. Patients may end treatment earlier than Day 10 if their symptoms subside following the criteria outline in the protocol section 4.1.

#### Follow-up Period

- For efficacy - patients will be followed up on Day 14 and Day 28. If patient is no longer hospitalized, follow-up will occur by phone-call.
- For safety - patients will be follow-up 28 days after the first treatment dose is administered. If patient is no longer hospitalized, follow-up will occur by phone-call.

Two interim analyses are planned to assess futility. The first IDMC interim analysis will take place after the first 60 participants have completed Day 10 of the study to evaluate whether the study will be stopped for futility based on change from baseline in room air SpO2. The second interim analysis will take place after 150 participants have completed Day 14 post-randomization based on event rate for the primary endpoint. The purpose of the second interim analysis will be futility as well as a potential sample size re-estimation in case the actual results differ from the original assumptions.

**Figure 1:** **Study Design**

[figure not shown]

TID=3 times daily

- 1 Participants may be discharged from hospital before Day 10.
- 2 Screening period may include Day 1, as participants may be screened and randomized on the same day provided all eligibility criteria are met.
- 3 The post-treatment efficacy and safety follow-ups may be conducted by telephone for participants who are discharged from the hospital at the time.

### 3.2 Determination of Sample Size

CCI

### 3.3 Endpoints

#### 3.3.1 Efficacy Variables

Primary:

- Proportion of participants who progress to level >4 of modified WHO ordinal scale due to COVID-19 by Day 14

Key Secondary:

- Change in room air SpO2 from baseline over time
- Change in NEWS 2 symptom score from baseline over time
- Change from baseline on the modified WHO ordinal scale at each visit up to Day 28
- Time to improvement to at least one level lower of the modified WHO ordinal scale
- Time to progression to at least one level higher of the modified WHO ordinal scale

Additional Secondary:

- Time to hospital discharge
- Incidence of mortality by Day 28

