All the categorical variables including the primary endpoint will be summarized by treatment in terms of the number of patients providing data at the relevant time point (n), frequency counts and percentages. Binary primary endpoint: (progression to critical stage/death up to Day 14) will be analyzed by a Cochran-Mantel-Haenszel (CMH) stratified for the factors used in the stratified randomization. Treatment difference will be tested using a Cochran–Mantel–Haenszel (CMH) test stratified by 1) country and 2) participant's clinical status at Baseline. For the categorical endpoints, relative risk and its 95% CI will be presented.

Percentages will be presented to one decimal place. Percentages will not be presented for zero counts. Percentages will be calculated using n as the denominator. If sample sizes are small, the data displays will show the percentages, but any textual report will describe frequencies only.

Changes from baseline in categorical data will be summarized using shift tables where appropriate.

P-values greater than or equal to 0.001, in general, will be presented to three decimal places. P-values less than 0.001 will be presented as “<0.001”.

Confidence intervals will be presented to one more decimal place than the raw data.

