## 4.9 Efficacy Evaluation

### 4.9.1 Analysis and Data Conventions

This study is designed to test for superiority. The null hypothesis for the treatment comparison will be that there is no difference in the rate of progression to at least one level higher of the modified WHO ordinal scale in RESP301 + SOC compared to SOC alone. The alternative hypothesis is that RESP301 +SOC reduces the rate of progression to at least one level higher in the modified WHO ordinal scale in COVID-19 at Day 14. Symbolically, this is expressed as follows:

$$\begin{aligned} H_0: p\text{WHO+1+RESP301+SOC} &\geq p\text{WHO+1+SOC} \\ H_a: p\text{WHO+1+RESP301+SOC} &< p\text{WHO+1+SOC} \end{aligned}$$

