### 4.9.2 Primary Efficacy Variable

Progression to level at least one level higher than baseline of modified WHO ordinal COVID-19 scale by Day 14”

The WHO 7-point ordinal scale is as follows:

1. Not hospitalized, no limitations on activities;
2. Not hospitalized, limitation on activities;
3. Hospitalized, not requiring supplemental oxygen;
4. Hospitalized, requiring supplemental oxygen;
5. Hospitalized, on non-invasive ventilation or high-flow oxygen devices;
6. Hospitalized, on invasive mechanical ventilation or ECMO;
7. Death.

The percentage and corresponding 95% CI of patients who progress to at least one level higher from baseline on the WHO 7-point ordinal scale on Day 14 will be summarized by treatment arm and overall. The odds ratio of RESP301 + SOC versus SOC alone and 95% CI intervals and p-values will be estimated using the CMH stratified by country and number of risk factors (as randomized).

WHO 7-point ordinal scale will be assessed daily while patient is hospitalized. Daily scores and changes from baseline will be summarized. Plots of mean score (with standard error bars) by treatment group over time may be produced.

A by-patient listing of the primary efficacy data will be provided

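### SAP version 2.0 defines the primary endpoint in two incompatible ways, so a move from level 3 to level 4 is an event in one section and not in another

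*SAP*

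**What the plan says.** All of this is current version 2.0 text. Section 3.1 enrols patients at WHO grades 3 and 4.

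- **2.1, primary objective:** prevent progression of "participants at level 3 or 4 in the modified World Health Organization (WHO) ordinal scale into higher levels".
- **3.3.1, endpoint list, under Primary:** "Proportion of participants who progress to level >4 of modified WHO ordinal scale due to COVID-19 by Day 14".
- **4.2, general presentation:** the binary primary endpoint is glossed as "progression to critical stage/death up to Day 14".
- **4.9.1, alternative hypothesis:** treatment "reduces the rate of progression to at least one level higher in the modified WHO ordinal scale in COVID-19 at Day 14".
- **4.9.2, primary variable:** "Progression to level at least one level higher than baseline of modified WHO ordinal COVID-19 scale by Day 14". The summary statistic in the same section is the percentage of "patients who progress to at least one level higher from baseline on the WHO 7-point ordinal scale on Day 14".

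On the scale printed in 4.9.2, level 3 is hospitalized without supplemental oxygen, level 4 is hospitalized with it, and levels 5 to 7 run from non-invasive ventilation or high-flow oxygen to death.

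**The concern.** While only level 4 patients were enrolled, as in SAP version 1.0, a level above 4 and one level above baseline were the same threshold. Adding level 3 separates them. The objective, hypotheses and primary-variable section of version 2.0 follow the one-level reading. The endpoint list keeps the fixed threshold and also requires attribution to COVID-19.

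The definition determines the event rate, the conditional power and sample size re-estimation at the second interim, and the primary test. The trial is open-label. If two definitions stand in the plan, the choice between them could be made after outcomes are visible. If the attribution clause were applied, cause would be judged with treatment known, and this SAP gives no rule for that judgement.

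**Working it through.** **1. Apply each wording to each case.**

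| Case | 3.3.1 | 4.9.1 / 4.9.2 | 4.2 |
|---|---|---|---|
| Level 3 to 4, no further | non-event | event | probably non-event; term undefined |
| Level 3 or 4 to level 5 or 6, due to COVID-19 | event | event | not certain |
| Death due to COVID-19 | event | event | event |
| Death not attributed to COVID-19 | non-event | event | event as worded |

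The first and last rows cannot be reconciled between 3.3.1 and 4.9.1/4.9.2. The hypothesis in 4.9.1 mentions COVID-19 as the disease setting; it does not make cause a condition for counting an event.

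**2. Timing.** 3.3.1 and the opening line of 4.9.2 count progression by Day 14. The summary statistic in 4.9.2 refers to status on Day 14, and 4.9.1 to at Day 14. A patient who worsens on Day 5 and is back at baseline level on Day 14 is an event if progression by Day 14 counts and a non-event under a status reading of the other two.

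**3. Reproduce the plan's own figures.** Inputs from Appendix A and 4.9.1.5: 50 vs 100 patients at the second interim, planned N = 300 (information fraction 0.5), final one-sided alpha 0.0249 (z = 1.9617).

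Z1 = (pC − pT) / √[pC(1−pC)/50 + pT(1−pT)/100]

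CP = Φ[(Z1/√0.5 − 1.9617)/√0.5]

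- 15/50 vs 15/100: Z1 = 2.027, CP = 90.0% (stated 90%, no increase).
- 10/50 vs 10/100: Z1 = 1.562, CP = 63.7% (stated 64%, required N 412).

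The unpooled variance reproduces the table. The pooled variance gives 94.0% for the 90% row. Unpooled variance is therefore used below.

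**4. What the definition can do at the second interim (assumed split of events).** Suppose the same 150 patients show 10/50 vs 10/100 at level >4, so that CP under 3.3.1 is 64% and N would rise to 412. Suppose a further 5 of 50 controls move only from 3 to 4.

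- If 5 of 100 treated patients do the same, the one-level counts are 15/50 vs 15/100: CP 90%, N stays at 300.
- If 10 of 100 treated patients do, the counts are 15/50 vs 20/100: Z1 = 0.10/√(0.0042 + 0.0016) = 1.313, CP = Φ[(1.857 − 1.9617)/0.7071] = 44%.

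**5. What it can do at the final test (assumed rates).** 100 vs 200 patients, fixed-sample normal approximation, one-sided 0.0249:

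Power = Φ[(pC − pT)/√(pC(1−pC)/100 + pT(1−pT)/200) − 1.9617]

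The one-level rates are the level >4 rates (20% vs 10%) plus a further 10% of controls, and 10% × RR of treated patients, who move only from 3 to 4.

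| Definition | RR for 3-to-4 moves | Control vs treated | Power |
|---|---|---|---|
| Level >4 | – | 20% vs 10% | Φ(0.100/0.0453 − 1.9617) ≈ 60% |
| One level | 0.5 | 30% vs 15% | Φ(0.150/0.0523 − 1.9617) ≈ 82% |
| One level | 0.75 | 30% vs 17.5% | Φ(0.125/0.0531 − 1.9617) ≈ 65% |
| One level | 1.0 | 30% vs 20% | Φ(0.100/0.0539 − 1.9617) ≈ 46% |

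**The case against.** The strongest defence is that the operative text is already clear. The hypotheses and the section headed primary efficacy variable agree with each other and with the objective, and 3.3.1 is only a list. A programmer would probably follow 4.9.2. Section 4.12 also points to an SAP addendum that is not shown and may settle the matter. This makes one-level worsening the better supported reading. It does not remove the conflict, because 3.3.1 is where the plan formally names its primary endpoint, and its wording differs in threshold and cause.

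It could also be said that level >4 was kept deliberately as primary, with one-level worsening reserved for the secondary time-to-progression endpoint in the same list. The tested hypothesis and the named primary variable rule that out.

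Three stronger readings are tempting and are not supported:

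- **Three incompatible definitions.** The critical stage in 4.2 is never mapped to the scale. It probably excludes level 4, and it may simply mean level >4. It is an undefined third wording, not a proven third endpoint.
- **The 3.3.1 definition costs power.** That follows only if treatment prevents 3-to-4 moves about as well as it prevents more severe progression. With no effect on those moves, the one-level definition has the lower power. The Appendix A rates do not decide it: they are hypothetical interim results, printed unchanged from version 1.0, when only level 4 patients were covered and the endpoint was level >4.
- **Unblinded attribution will remove events.** Nothing in this SAP describes an attribution step, and 4.9.1 and 4.9.2 omit the clause. It is a risk only if the 3.3.1 wording is applied.

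**Conclusion.** The contradiction is certain and lies wholly within version 2.0. Sections 3.3.1 and 4.9.1/4.9.2 classify a 3-to-4 move and a death not attributed to COVID-19 differently. The by, on and at Day 14 wordings leave a transient worsening unclassified. It must be fixed, because it concerns the confirmatory endpoint.

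Its numerical effect cannot be fixed from the documents: the sample size sections are redacted and no rates by baseline level are given. On the assumed rates, final power under the one-level definition ranges from about 46% to 82%, against about 60% for level >4. Interim conditional power ranges from 44% to 90%, against 64%. These ranges rest on the assumed 20% vs 10% rates, the assumed 10% of controls moving only from 3 to 4, and a relative risk of 0.5 to 1.0 for those moves. They show that the choice matters, not which definition is favoured.

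**What to change.** Use one definition in 3.3.1, 4.2, 4.9.1 and 4.9.2: worsening by at least one level from baseline on the modified WHO scale, including death from any cause, at any time by Day 14. This follows the SAP's own objective, hypotheses and primary-variable section.

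- Replace the primary bullet in 3.3.1, including its attribution clause.
- Replace the parenthesis in 4.2.
- Change the on and at Day 14 wordings in 4.9.2 and 4.9.1 to by Day 14.
- Confirm the result against protocol 4.0, which the SAP cites as its basis and which is not at hand. If the protocol carries the attribution clause or the fixed threshold, reconcile the two documents.

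Optionally, report progression to level >4 as a named sensitivity analysis and tabulate primary events by baseline level (3 vs 4). The contradiction can be cured without either.

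Cost: SAP wording, plus one sensitivity analysis and one table if the optional items are taken up. No new data are needed.

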#### 3.3.2 Safety Variables

- Clinical safety laboratory measurements
- Physical examinations
- Vital signs
- Concomitant medications
- Cumulative incidence of AEs and Severe AEs

CCI  
CCI  
CCI

CONFIDENTIAL

Project Document Version No. 2.0  
Project Document Effective Date: Date of last signature  
Page 11 of 31

- Incidence of participants unable to tolerate nebulization due to:
  - Reduction in SpO2 to < 90%, unless well clinically tolerated according to Investigator's opinion
  - Other clinical signs of intolerance according to Investigator's opinion
- Incidence of clinical bronchial hyper-responsiveness related to nebulization

### 3.4 Exploratory Variables

- CCI

## 4 STATISTICAL METHODS

### 4.1 Data Quality Assurance

All tables, figures and data listings to be included in the report will be independently checked for consistency, integrity and in accordance with standard PAREXEL procedures.

### 4.2 General Presentation Considerations

Baseline is the last available pre-treatment assessment. All assessments should have time collected. If time is not collected and date of assessment is the same as the *first dose date*, then assessment will be assumed to be collected prior to treatment unless schedule of assessments and protocol indicate planned collection is always after dosing.

Day-of-Discharge (DoD) is the day when patient is discharged from the hospital.

Durations are calculated as the stop date minus the start date plus one.

For elapsed time (e.g. time since the initial diagnosis), if the reference date is on or after the event date, then the elapsed time is the reference date minus the event date plus one. If the reference date is before the event date, then the elapsed time is the reference date minus the event date.

If more than one laboratory value is available for a given study day, the first valid observation will be used in summaries and all observations will be presented in listings. If it is not possible to determine which is the first measurement due to missing times, then the average of all measurements for that time point will be used as the value for that time point.

Continuous data will be summarized in terms of the mean, standard deviation (SD), median, minimum, maximum and number of observations, unless otherwise stated. Continuous data that are expected to be skewed will be presented in terms of the maximum, upper quartile, median, lower quartile, minimum and number of observations. The minimum and maximum will be reported to the same number of decimal places as the raw data recorded in the database. The mean, median, lower quartile and upper quartile will be reported to one more decimal place than the raw data recorded in the database. The SD will be reported to two more decimal places than the raw

---

data recorded in the database. In general, the maximum number of decimal places reported shall be four for any summary statistic.

The mixed model with repeated measurements /analysis of covariance model with treatment, country, participant's clinical status at Baseline and visit as the model term, and Baseline value as the covariate will be used to test for the significance of the treatment difference. Least square means, standard errors, 95% CIs and p-values will be presented.

All the categorical variables including the primary endpoint will be summarized by treatment in terms of the number of patients providing data at the relevant time point (n), frequency counts and percentages. Binary primary endpoint: (progression to critical stage/death up to Day 14) will be analyzed by a Cochran-Mantel-Haenszel (CMH) stratified for the factors used in the stratified randomization. Treatment difference will be tested using a Cochran–Mantel–Haenszel (CMH) test stratified by 1) country and 2) participant's clinical status at Baseline. For the categorical endpoints, relative risk and its 95% CI will be presented.

Percentages will be presented to one decimal place. Percentages will not be presented for zero counts. Percentages will be calculated using n as the denominator. If sample sizes are small, the data displays will show the percentages, but any textual report will describe frequencies only.

Changes from baseline in categorical data will be summarized using shift tables where appropriate.

P-values greater than or equal to 0.001, in general, will be presented to three decimal places. P-values less than 0.001 will be presented as “<0.001”.

Confidence intervals will be presented to one more decimal place than the raw data.

